### 6.5.1 Adverse Events

Summaries and listings of SAEs and Serious TEAEs include SAEs upgraded by the sponsor based on review of the Sponsor's list of Always Serious terms or upgraded according to the Important Medical Event process, if any upgrade was done.

The coding dictionary for this study will be MedDRA. It will be used to summarize AEs by System Organ Class (SOC) and Preferred Term (PT).

An overview table will include the following details:

- Number of TEAEs,
- Number and percentage of subjects with TEAEs,
- Number of drug related TEAEs,
- Number and percentage of subjects with drug related TEAEs,
- Number of serious TEAEs,
- Number and percentage of subjects with serious TEAEs,
- Number of serious drug related TEAEs,
- Number and percentage of subjects with serious drug related TEAEs,
- Number of TEAEs leading to withdrawal of treatment,
- Number and percentage of subjects with TEAEs leading to withdrawal of treatment,
- Number of drug-related TEAEs leading to withdrawal of treatment,
- Number and percentage of subjects with drug-related TEAEs leading to withdrawal of treatment,
- Number of TEAEs leading to death,
- Number and percentage of subjects with TEAEs leading to death,
- Number of drug-related TEAEs leading the death,
- Number and percentage of subjects with drug-related TEAEs leading to death, and
- Number and percentage of subjects who died.

The number and percentage of subjects with TEAEs, as classified by SOC and PT will be summarized for each treatment group. Summaries will be provided for:

- TEAEs,
- Drug related TEAEs,
- Serious TEAEs,
- Drug related serious TEAEs,
- TEAEs leading to withdrawal of treatment,
- Drug related TEAEs leading to withdrawal of treatment,
- Frequently Reported (>=5% in Any Treatment Group) TEAEs Excluding SAEs

The number and percentage of subjects with TEAEs, as classified by PT only, will be summarized for each treatment group.

The number of TEAEs and the number and percentage of subjects with TEAEs, as classified by SOC and PT will also be summarized by severity and by relationship to study drug. In the subject count, if a subject has multiple TEAEs with the same SOC or PT, but with differing severity or relationship, then the subject will be counted only once with the worst severity and highest degree of relationship, however, if any of the severity or relationship values are missing then the subject will be counted only once with missing severity or relationship. In the adverse event count, the adverse events will be presented in each category they were classified to. Drug related TEAEs will be presented in a similar way by severity only.

Adverse events of interest will be tabulated by PT.

AEs will be provided in listing format by site and subject for the SAF.

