## 2.2 Study Design

[figure not shown]
The study follows an open-label, randomized, 12-week, prospective, interventional postauthorization design for the treatment of OAB in approximately 249 Chinese subjects. Each subject will participate in one 12-week treatment period.

This study is designed to support the Imported Drug License (IDL) renewal and mirabegron safety surveillance in China. The data-cut with summaries and the planned primary analysis for the end of this study will be used for IDL renewal. Subjects fulfilling the screening inclusion/exclusion criteria will be randomized in 2:1 ratio to 50 mg mirabegron and 25 mg mirabegron using a computer-generated randomization to reduce selection bias. Treatments will be administered once daily orally after meal during a 12-week, open-label treatment period. Study visits will take place at weeks 4, 8 and 12. For 25 mg mirabegron group, a dose escalation to 50 mg is permitted on visit 3 and visit 4 according to investigators' discretion.

Planned total number of study sites include approximately 10 study sites across China.

Figure 1 presents the study schema.

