## 4.4 Safety Analysis Set

The Safety Analysis Set (SAF) will consist of all subjects who took at least 1 dose of IP. The safety set will be analyzed by treatment arm as treated (i.e., based on the treatment the subject actually received rather than the treatment to which the subject was randomized).

The SAF will be used for summaries of demographic and baseline characteristics and all safety- and tolerability-related variables.

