## 5.5 Other Endpoints

### 5.5.1 Exposure to Study Drug

The duration of exposure to each dose of study drug (Mirabegron 25 mg and Mirabegron 50 mg) by visit and for the whole period will be calculated using the following information :

- Overall start date and stop date of the study medication. The first dose of study drug is to be administered on Day 1, the day on visit 2/week 0 [baseline]. Treatment will be administered once daily orally after meal during a 12-week, open-label treatment period.
- Start date and new dose of study drug at each titration step. At visit 3/week 4 or visit 4/week 8 the dose may be up-titrated (from 25 to 50 mg according to investigators' discretion), or may remain the same. The study does not allow dose reduction from 50 mg to 25 mg as the former is considered a safe and effective recommended dose.

- Start date and new dose of study drug after each unscheduled dose change.
- At any time during the treatment period, the subject may have an unscheduled dose interruption. At each unscheduled change in dose, the (new) dose, start date and reason are recorded.

In all cases where there is a dose change, either because of dose titration or an unscheduled dose interruption, the first and the last dose of the medication at the old level will be collected at the CRF. In this way, the subject's dosing history can be reduced to a series of unbroken intervals within each of which, the dose level is constant. From these, the subject's exposure at each dose can be calculated.

To illustrate, consider a subject with the following dose information on the eCRF:

- The dates of the very first and very last dose of the study medication given at  $D_1=1^{st}$  July 2020,  $D_{last}=23^{rd}$  September 2020.
- Up-titration to 50 mg at Visit 3. The first dose at the new level is given at  $D_2=29^{th}$  July 2020.
- Study drug interrupted at an unscheduled visit. The date of last dose is given at D3=1st August 2020.
- Study drug re-started at an unscheduled visit at  $D_4=5^{th}$  August 2020.
- Remains at 50 mg till Visit 5 (Dlast=23rd September 2020).

From these dates we calculate the following:

- The duration of exposure to the treatment can be calculated as  $E_{TOT}=D_{last}-D_1+1-(D_4-D_3-1)$ =82 days.

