### 6.5 Analysis of Safety

Safety analysis will be conducted on the SAF. Safety endpoints will be summarized by treatment group and visit, if applicable. Descriptive statistics will be presented.

All safety summaries (except for shift tables in Sections 6.5.2 and 6.5.4) will be presented by the following:

- Mirabegron 25 mg
  - Never Up-Titrated
  - Later Up-Titrated to 50 mg (at visit 3 or 4)
  - Total
- Mirabegron 50 mg
  - $\circ$  as Randomized
  - Up-Titrated from 25 mg (at visit 3 or 4)
  - Total
- Total Mirabegron, i.e., the sum of the Mirabegron 25 mg (Total) and of Mirabegron 50 mg (As-Randomized)

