#### 6.10.2 Imputation Rules for Incomplete Dates

As a general principle, no imputation of missing data for variables will be done. Exceptions are the start and stop dates of AEs and concomitant medication. The imputed dates will be used to allocate the concomitant medication and AEs to a treatment group, in addition to

determining whether an AE is/is not treatment emergent. Listings of the AEs and concomitant medications will present the actual partial dates; imputed dates will not be shown.

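### Crude TEAE percentages are shown in dose columns with unequal time at risk, so the columns that contain escalated subjects read lower than randomised 50 mg even at an equal event hazard

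*SAP*

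**What the plan says.** Treatment is planned for 12 weeks (SAP 2.2: "Treatments will be administered once daily orally after meal during a 12-week, open-label treatment period"), and a subject randomised to 25 mg may move to 50 mg at Week 4 or Week 8.

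SAP 6.5 presents all safety summaries except the shift tables in seven columns. A subject who escalates appears in two of them, "Later Up-Titrated to 50 mg (at visit 3 or 4)" under 25 mg and "Up-Titrated from 25 mg (at visit 3 or 4)" under 50 mg. Each part also feeds the total for its dose. The seventh column is "Total Mirabegron, i.e., the sum of the Mirabegron 25 mg (Total) and of Mirabegron 50 mg (As-Randomized)".

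For adverse events, SAP 6.5.1 plans that "The number and percentage of subjects with TEAEs, as classified by SOC and PT will be summarized for each treatment group", plus event counts in the overview. Protocol 9.4.3.1 also plans numbers and percentages only. Neither document plans a rate per subject-time, a time-to-first-event summary or an adverse event table over a common window.

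No rule states outright which column receives an event in an escalated subject. SAP 4.4 says "The safety set will be analyzed by treatment arm as treated", which does not settle it. SAP 6.10.2 comes closest: "The imputed dates will be used to allocate the concomitant medication and AEs to a treatment group". SAP 5.4.1 counts TEAEs until 30 days after the last dose. SAP 5.5.1 derives "The duration of exposure to each dose of study drug", counting dosing days only, and SAP 6.3 tabulates exposure separately, by the same dose groups.

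**The concern.** A crude percentage grows with the time over which a subject can have an event. If an escalated subject's time is cut at the switch, each part covers only some of the 12 weeks, while a subject randomised to 50 mg contributes all of it. The shorter columns then show fewer subjects with events for a reason that has nothing to do with dose.

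The starting dose is one of the questions that the regulator asked (Protocol 2 and 2.1). The events of special interest include raised heart rate, raised blood pressure and QT prolongation, and Protocol 2.3.1 links these potential risks to rising exposure at supratherapeutic doses. A reader of the planned tables could take a gap created by unequal time at risk for a dose response.

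**Working it through.** **1. Do the columns split time by dose?** Three places imply it. SAP 6.10.2 allocates events by date. The exposure example in SAP 5.5.1 cuts the subject's time at the switch. SAP 6.5.2 names the groups with both a baseline and a Week 12 laboratory value and leaves out the later-up-titrated group, which fits a column that ends at escalation. If time were not split, the two escalation columns would hold the same events.

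**2. Reproduce the plan's own figure.** The SAP 5.5.1 example starts on 1 July 2020, first takes 50 mg on 29 July, stops after 1 August, restarts on 5 August and ends on 23 September.
- 25 mg: 1 to 28 July = 28 days.
- 50 mg: 4 + 50 = 54 days.
- Total: 28 + 54 = 82 days.

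All three agree with the SAP. The documents give no figure for TEAE percentages.

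**3. Time at risk.** Twelve weeks are 84 dosing days, and the TEAE window is 84 + 30 = 114 days. The tail is assigned to the last dose.

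| Part | Dosing days | TEAE days |
|---|---|---|
| 50 mg as randomised; 25 mg never up-titrated | 84 | 114 |
| 25 mg before Week 4 switch | 28 | 28 |
| 25 mg before Week 8 switch | 56 | 56 |
| 50 mg after Week 4 switch | 56 | 86 |
| 50 mg after Week 8 switch | 28 | 58 |

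On the TEAE window, randomised 50 mg has up to 114/28 = 4.1 times the time of a 25 mg part, and up to 114/58 = 2.0 times that of an up-titrated 50 mg part.

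**4. Crude percentages at an equal hazard.** Assumed, not in the documents: a constant hazard h that is equal on both doses, 30% incidence over 114 days, and the escalation shares below.

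h = −ln(0.7)/114 = 0.00313 per day, and p(t) = 1 − exp(−h·t).

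p(28) = 8.4%, p(56) = 16.1%, p(58) = 16.6%, p(86) = 23.6%, p(114) = 30.0%.

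With 50% escalating at Week 4, 25% at Week 8 and 25% never:
- 25 mg total: 0.50 × 8.4 + 0.25 × 16.1 + 0.25 × 30.0 = 15.7%.
- 50 mg up-titrated: (0.50 × 23.6 + 0.25 × 16.6)/0.75 = 21.3%.
- 50 mg as randomised: 30.0%.
- 50 mg total: 249 subjects at 2:1 are 166 and 83, and 75% of 83 is 62.25. So (166 × 30.0 + 62.25 × 21.3)/228.25 = 27.6%.

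With 10% escalating at each visit, 25 mg total is 0.10 × 8.4 + 0.10 × 16.1 + 0.80 × 30.0 = 26.4%. With no escalation it is 30.0%.

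**5. Would the exposure in SAP 5.5.1 serve as the denominator?** No. It holds dosing days, whereas the numerator includes events in the 30-day tail. Under step 4's first scenario:
- Randomised 50 mg: 30.0/84 = 0.357 per 100 dosing days.
- Up-titrated 50 mg: mean dosing time (0.50 × 56 + 0.25 × 28)/0.75 = 46.7 days, so 21.3/46.7 = 0.456, or 1.28 times randomised 50 mg.
- After a Week 8 switch only: 16.6/28 = 0.593, or 1.66 times.
- 25 mg total: mean dosing time 0.50 × 28 + 0.25 × 56 + 0.25 × 84 = 49 days, so 15.7/49 = 0.321, or 0.90 times.

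Equal hazards still look unequal, and for up-titrated 50 mg the error changes direction.

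**6. Does time to first event serve?** Under a constant hazard the expected time at risk up to the first event or the end of the part is p(t)/h, so events over time return h in every column. Here that is 0.00313 × 365.25 × 100, about 114 per 100 subject-years. This relies on the hazard being constant. With early-loaded events (Weibull shape 0.5, 20% over 84 days, tail ignored), the same rate relative to randomised 50 mg is 1.70 for 25 mg before a Week 4 switch, and 0.61 or 0.53 for 50 mg after a Week 4 or Week 8 switch. The crude percentages in that case are 12.1% for 25 mg before a Week 4 switch and 9.0% or 4.0% for 50 mg after it, against 20%, so they remain too low.

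**The case against.** The strongest reply is that the plan already lets a careful reader see the imbalance. Exposure is tabulated for the same dose groups, the overview gives event counts, and events are listed by subject. Safety is descriptive with no between-dose test, and Protocol 4.3 makes 50 mg the primary safety assessment and 25 mg exploratory. This stands as a limit on importance: no error rate is affected. It does not remove the distortion, because nothing links the exposure table to the percentages.

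A second reply is that the split by dose is implied and not written. That also stands. If the 25 mg total were meant to count every event in the randomised arm whatever the dose at onset, that column would not be shortened, although the two escalation columns would be. The opposite reading has its own cost: if 25 mg total counts only events on 25 mg, the overall mirabegron column, defined as a sum that leaves out the up-titrated part, omits events that begin after escalation. Either way a rule is needed.

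A third reply is that a rate per time on dose is not a clean remedy. It assumes a roughly constant hazard (step 6), and it cannot correct for selection: escalated subjects have already taken 25 mg for 4 or 8 weeks and were chosen at the investigator's discretion. Nor does it compare starting doses, which is what the regulator asked about. All of this stands and shapes the fix.

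**Conclusion.** The point holds as a matter of presentation and is a low-cost improvement. Crude percentages read too low in the later-up-titrated 25 mg, 25 mg total and up-titrated 50 mg columns, and slightly too low in 50 mg total. With 30% incidence over 114 days, the 25 mg total falls to 16% under heavy escalation and to 26% when 10% escalate at each visit. Up-titrated 50 mg reads 21% under the heavy scenario. These sizes rest on an assumed equal constant hazard, assumed escalation shares and allocation by dose at onset. With no escalation the distortion is zero.

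A reader might infer two stronger things that the documents do not support. One is that 25 mg as such is made to look safer. The never-up-titrated column keeps the full planned period and is shown separately. The other is that dividing by the exposure already derived in SAP 5.5.1 would settle dose comparisons. Step 5 shows that it would not, because those are dosing days and the TEAE window runs 30 days longer.

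**What to change.** In the overview, special-interest and common-TEAE tables:

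(a) State that each event is allocated to the dose at onset, with the 30-day tail assigned to the last dose.

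(b) Beside the percentages, show subjects with a first TEAE in that column per subject-time at risk. Time runs from the start of that dose to the first event, the escalation, or 30 days after the last dose, whichever comes first. Do not use the dosing days of SAP 5.5.1.

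(c) Add a summary by randomised starting dose over the whole TEAE window, regardless of escalation, and use it for any comparison of starting doses.

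Nothing planned is removed and no new data are collected. The cost is more than one column: SAP 6.5 has seven treatment columns, and the common-TEAE table needs time to first event for each preferred term, which the SAP does not derive at present. The rate in (b) should be labelled supportive and descriptive, since it assumes a roughly constant hazard and does not remove selection of who is escalated.

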7.3 Adverse Events and Other Safety Aspects

The definitions of an AE or SAE can be found in [Sections 10.3.1 Definition of Adverse Events and 10.3.2 Definition of Serious Adverse Events], respectively.

AEs will be reported by the subject.

The investigator and any qualified designees are responsible for detecting, documenting and recording events that meet the definition of an AE or SAE and remain responsible for following up AEs that are serious, considered related to the study IP, or that caused the subject to discontinue the IP and/or study [Section 10.3 Appendix 3 Adverse Events: Definitions and Procedures for Recording, Evaluating, Follow-up and Reporting].

The method of recording, evaluating, and assessing causality of AE and SAE and the procedures for completing and transmitting SAE reports are provided in [Section 10.3 Appendix 3 Adverse Events: Definitions and Procedures for Recording, Evaluating, Follow-up and Reporting].

7.3.1 Time Period and Frequency for Collecting Adverse Event and Serious Adverse Event Information

All SAEs will be collected from the signing of the ICF until 30 days after the final IP administration or when the subject is determined to be a screen failure and reported in the eCRF.

All AEs will be collected from the signing of the ICF until 30 days after the final IP administration or when the subject is determined to be a screen failure and reported in the eCRF.

If the severity of an SAE/AE changes, the event should be relisted in the eCRF with the new severity and new onset date.

If the severity decreases, the SAE/AE should be relisted in the eCRF with the new severity and new onset date. The exception is ongoing pre-dose events that continue post-dose and improve post-dose. Such events should not be re-listed.

If the severity of an SAE reduces, the details of the AE should be provided on the SAE worksheet for the medical assessor to be able to assess the course of the event.

All SAEs will be recorded and reported to the sponsor or designee immediately and under no circumstance should this exceed 24 hours, as indicated in [Section 10.3 Appendix 3 Adverse Events: Definitions and Procedures for Recording, Evaluating, Follow-up and Reporting]. The investigator will submit any updated SAE data to the sponsor within 24 hours of it being available.

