9.4.3.1 Adverse Events

AEs will be coded using MedDRA. A TEAE is defined as an AE observed after starting administration of the IP and 30 days after the final administration of IP. An IP-related TEAE is defined as any TEAE with a causal relationship assessed as "yes" by the investigator.

The number and percentage of subjects with TEAEs, drug-related TEAEs, serious TEAEs, drug-related serious TEAEs, TEAEs leading to leading to withdrawal of treatment and drug-related TEAEs leading to leading to withdrawal of treatment as well as TEAEs of special interest [Section 7.3.6 Adverse Events of Special Interest] will be summarized by SOC, preferred term and treatment group. The number and percentage of TEAEs by severity will also be summarized. The worst severity will be summarized if the same AE is recorded more than once for a subject.

AE data will be listed.

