### 5.4.1 Adverse Events

AEs will be coded using MedDRA. A TEAE is defined as an AE observed after starting administration of the IP until 30 days after the final administration of IP. If the adverse event occurs on Day 1 and the onset check box on the (AE) eCRF is marked "Onset after first dose of study drug" or the onset check box is left blank, then the adverse event will be considered treatment emergent. If the adverse event occurs on Day 1 and the onset check box is marked "Onset before first dose of study drug", then the adverse event will not be considered treatment emergent. If a subject experiences an event both during the pre-investigational period and during the investigational period, the event will be considered as TEAE only if it has worsened in severity (i.e., it is reported with a new start date).

A drug-related TEAE is defined as any TEAE with at least possible relationship to study treatment as assessed by the investigator or with missing assessment of the causal relationship.

AEs may be upgraded by the sponsor according to the Important Medical Event process.

A drug-related TEAE is defined as any TEAE with at least a possible relationship to study treatment as assessed by the investigator or with a missing assessment of the causal relationship.

Common TEAEs are defined as preferred terms (PTs) that have been reported by at least 5% of the subjects, in any treatment group.

When an AE start or stop date is missing, the date will be imputed using the rules in Section 6.10.2.2.

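### In the by-severity subject counts of SAP 6.5.1, one missing grade moves a subject with a known severe TEAE from severe to missing, so these counts can only understate severe TEAEs

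*SAP*

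**What the plan says.** SAP 6.5.1 (Adverse Events) specifies tables of TEAEs by SOC and PT, split by severity and by relationship, with both event counts and subject counts. A subject with several TEAEs in the same SOC or PT is handled in two steps. First, "then the subject will be counted only once with the worst severity and highest degree of relationship". Then comes an exception: "if any of the severity or relationship values are missing then the subject will be counted only once with missing severity or relationship". I read this as applying to each attribute separately, so that a missing severity affects the severity table and a missing relationship affects the relationship table.

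The event counts follow a different rule: "In the adverse event count, the adverse events will be presented in each category they were classified to". The severity rule also carries over to a further table: "Drug related TEAEs will be presented in a similar way by severity only".

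Protocol 9.4.3.1 says of severity: "The worst severity will be summarized if the same AE is recorded more than once for a subject". It makes no exception for missing grades. Protocol 10.3.4 has three grades, of which severe is the highest.

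On causality, SAP 5.4.1 defines a drug-related TEAE as one at least possibly related, "or with missing assessment of the causal relationship".

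**The concern.** AE severity is part of a stated secondary safety endpoint (Protocol section 3; SAP 2.1). The SAP 6.5.1 overview table has no row for severe TEAEs, and AEs of interest are tabulated by PT only. The by-severity tables are therefore the only specified summaries that say how many subjects had a severe event, and they are the ones the exception alters.

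A missing grade normally leaves the worst severity uncertain. When another record in the same cell is already severe, nothing is uncertain, because no unknown grade could be worse. The exception discards that knowledge. It never moves a subject into the severe row, so any error is an understatement. The rule also works at SOC level, where an ungraded event under a different PT is enough to displace a known severe one.

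**Working it through.** The documents state no figure on this point, so there is nothing to reproduce. The check applies the SAP rule and a worst-recorded-grade rule to the same example records.

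**Severity, one subject, one SOC or PT**

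| Recorded severities | SAP 6.5.1 | Worst recorded grade |
|---|---|---|
| severe | severe | severe |
| severe, mild | severe | severe |
| severe, missing | **missing** | **severe** |
| mild, missing | missing | mild |
| missing only | missing | missing |

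The third row is the fault. The fourth differs too, but there the true worst grade really is unknown.

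**SOC against PT.** Suppose a subject has PT A graded severe and PT B ungraded, both in one SOC. The PT A row counts the subject as severe, while the SOC row above it counts the subject as missing. The severe count for a SOC can thus be smaller than that of a PT inside it.

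**Relationship, same exercise.** Protocol 10.3.3 records causality as yes or no.

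| Recorded relationships | Row in SAP 6.5.1 by-relationship table | Drug-related under SAP 5.4.1? |
|---|---|---|
| yes, no | related | yes |
| yes, missing | missing | yes |
| no, missing | missing | yes |
| missing only | missing | yes |
| no only | not related | no |

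Every subject in the related or the missing row is drug-related under 5.4.1, and no other subject is. Hence, at each SOC or PT, related + missing = drug-related. The tables reconcile.

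**Size of one displaced subject.** Planned numbers are 166 on 50 mg (Protocol 9.2) and 249 − 166 = 83 on 25 mg.
- 50 mg: 1/166 = 0.6 percentage points.
- 25 mg: 1/83 = 1.2 percentage points.

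These are planned randomized numbers, not SAF counts. SAP 6.5 also splits 25 mg into never and later up-titrated, where the denominators are smaller and one subject weighs more.

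**How often it could happen (assumption, for illustration).** Let m be the chance that a grade is missing, independent across records, and k the number of other records in the same SOC or PT. A subject with a known severe record is displaced with probability 1 − (1 − m)^k. The documents give neither m nor k.

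| m | k = 1 | k = 4 |
|---|---|---|
| 0.5% | 0.5% | 1 − 0.995^4 = 2.0% |
| 1% | 1.0% | 1 − 0.99^4 = 3.9% |
| 2% | 2.0% | 1 − 0.98^4 = 7.8% |
| 5% | 5.0% | 1 − 0.95^4 = 18.5% |

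With m = 0 the probability is 0. Under the worst-recorded-grade rule it is 0 for every m.

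**The case against.** The strongest defence is that the rule is visible and rarely active. Displaced subjects appear in a missing row that any reader can see. Investigators must grade every AE (Protocol 10.3.4) and the sponsor quality-checks the data (Protocol 10.1.7), so missing grades should be few and may be none at lock. This limits the practical effect, but it does not justify the clause, which operates only when grades are missing and then discards a known one. Nor does the no-imputation principle in SAP 6.10.2 help, since using the worst recorded grade imputes nothing.

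A second defence is that showing missing is the honest display for a subject with a mild and an ungraded event, who may have had a severe one. That stands, and the fix has to deal with it.

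A third is that Protocol 9.4.3.1 speaks only of the same AE recorded more than once, is silent on missing values, and leaves analysis details to the SAP (Protocol 9.4). This stands in part. The departure is clear for repeat records of one AE, reaches different PTs within a SOC only by extension, and does not concern causality at all.

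Three stronger readings are tempting, and the documents do not support them.
- *The severe event disappears from the TEAE tables.* It does not. It stays in the severe event count of the same table, in the other TEAE tables where it qualifies, and in the AE listing.
- *Related TEAEs are understated and the causality tables disagree.* They are not and do not. Missing causality counts as drug-related under SAP 5.4.1, and the rows sum exactly as shown above.
- *Relisting an AE when its severity changes makes displacement more likely.* Protocol 7.3.1 says "If the severity of an SAE/AE changes, the event should be relisted in the eCRF with the new severity and new onset date". Relisting is prompted by a known new grade, so it gives no reason to expect ungraded records.

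**Conclusion.** The point holds for severity, and only for the subject counts in the by-severity tables, for all TEAEs and for drug-related TEAEs. There the SAP places a subject whose worst grade is known to be severe in the missing row. The error runs one way and affects a secondary safety endpoint. For repeat records of the same AE it departs from the protocol.

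The size is 0.6 percentage points per displaced subject on 50 mg and 1.2 on 25 mg, on planned numbers. How many subjects would be displaced cannot be derived from the documents; the probabilities above rest on assumed missing rates and independence, and the effect is nil if all grades are complete. The primary analysis and all hypothesis tests are untouched. The change is worth making because the rule is wrong whenever it bites on a severe event and costs almost nothing to correct.

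**What to change.** Separate severity from relationship in SAP 6.5.1 and replace the severity part of the exception with wording such as: *In the tables by severity, a subject is counted once per SOC or PT at the worst recorded severity, and always as severe if any record is severe; missing is used only when no severity is recorded.*

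The small downside is that a subject with a mild or moderate event and an ungraded one is shown at the known grade, which may be too low. A footnote giving the number of counted subjects who also have an ungraded event keeps that uncertainty visible.

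Leave the relationship rule as it is. An optional footnote can say that the missing row counts as drug-related under SAP 5.4.1.

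The cost is one sentence, one footnote and a small programming change, with no new data. SAP section 1 allows revision before hard lock; after that, the change would be documented in the CSR.
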